## 1. INTRODUCTION

This document details the statistical analysis of the data that will be performed by for the US WorldMeds, LLC study USWM-LX1-3003-2.

The proposed analysis is based on the contents of the Final Version of the protocol (dated 03-Feb-2012) and amendments 1 and 2 (dated 22-Jan-2015 and 21-May-2015 respectively).

The primary objective of the study is to continue to investigate the safety of lofexidine when administered for at least 7 days at clinically relevant doses (3.2 or 2.4 mg/day) to alleviate symptoms of acute withdrawal from opioids in a variety of clinical scenarios in both in-clinic and outpatient settings. The effectiveness of lofexidine is also of interest.

Table 1. Schedule of Study Assessments

Activity	Screening	Baseline (a)	In-clinic Treatment	In-clinic/Outpatient Treatment	Outpatient Treatment	Study Discontinuation/ End of Study*
	Days -8 to -1	Day 1	Days 1-3	Days 4-7	Days 8-14	
Informed Consent Signed	X					
Subject Number Assigned	X					
Inclusion/Exclusion Criteria	X	X (b)				
Prior Medication History	Past 30 days	X (b)				
Demographics	X					
Medical and Smoking History	X					
Mini-International Neuropsychiatric Interview	X					
Infectious Disease Assessments (c)	X					
Chest X-Ray (c)	X					
Pregnancy Test (d)	X	X				X
Height	X					
Weight	X					X
Complete Physical Exam	X	X (b)	X (e)	As needed	As needed	X
Admission to In-clinic Facility		X (f)				
Study Medication Administration			X (QID)	X (QID) (g)	Optional	
Medication Compliance			X	X	X	X
Study Medication Taper					X	
Discharge from In-clinic Facility				Variable, but by Day 7		
Clinic Visit				Daily if outpatient	Daily	
Issue Subject Diary				Daily if outpatient	Daily	
12-Lead Electrocardiogram (duplicate)	X (h)	X (i)	X (i)			X (j)
Urine Drug Screen (k)	X	X	X	X	X	X
Vital Signs (Sitting/Recumbent & Standing BP and pulse; respiration; and temperature)	X	X	X (l)	X (l) (m)	X (m)	X
Clinical Laboratory Tests (hematology, chemistry, urinalysis)	X	As needed	As needed	As needed	As needed	X
Adverse Events Assessment			X	X	X	X
C-SSRS Baseline Version		X				
C-SSRS Since Last Visit Version			X (n)	X (n)	X (n)	X
Short Opiate Withdrawal Scale of Gossop (o)		X	X	X	X	X
Clinical Opiate Withdrawal Scale (COWS) (o)		X	X	X	X	X
Fingerprick Blood Sample			X (p)	X (q)	X (p) (q)	X (p)
Concomitant Medications Assessment			X	X	X	X

Table 1. Schedule of Study Assessments

Activity	Screening	Baseline (a)	In-clinic Treatment	In-clinic/Outpatient Treatment	Outpatient Treatment	Study Discontinuation/ End of Study*
	Days -8 to -1	Day 1	Days 1-3	Days 4-7	Days 8-14	
Define Subject-Specific Withdrawal Treatment Goal	X					
Assessment of Completion of Pre-defined Withdrawal Treatment Goal (r)			X	X	X	X
Telephone Follow Up Contact						X (s)

**Abbreviations:** BP = blood pressure, C-SSRS = Columbia Suicide Severity Scale, PK = pharmacokinetic, PPD = purified protein derivative, QID = 4 times daily

\* The study discontinuation/end of study assessments/procedures should always be done when subject exits from the study. (a)

The Baseline period is the morning of admission, before dosing.

- (b) This form is to be updated at Baseline.
- (c) A chest x-ray is required only if a PPD skin test for tuberculosis is not done, the current PPD is positive, or if a past PPD was positive.
- (d) The urine sample collected on the first day of screening will be divided into two aliquots. One sample will be sent to the central lab urinalysis and the other sample will be used for urine drug screening and immediate "dipstick" analysis of pregnancy (females only). ) for
- (e) A complete physical exam will be done on Day 1 (3-4 hours after first dose) and as clinically warranted.
- (f) Subjects may be admitted to the hospital or clinic in the evening (Day -1) before study drug administration on Day 1.
- (g) Per Investigator judgment, subjects can be discharged from the study after receipt of at least one dose of study drug on Day 7 and after completion of all end-of-study procedures.
- (h) Baseline 12-lead electrocardiograms (ECGs) will be done on one day during the screening period at 8 AM (or as close to 8 AM as possible) and at 11:30 AM. Note that a time delay for the 8 AM ECG will not be considered a protocol deviation, but that the second ECG should be taken 3.5 hours after the first ECG.
- (i) 12-lead ECGs (duplicate) before dosing on Day 1 at 8 AM and 3.5 hours ( $\pm$  15 minutes) after dosing.
- (j) 12-lead ECGs (duplicate) before subject's last dose and 3.5 hours after dosing (or as close to this time as possible) or, if applicable, at discontinuation from the study.
- (k) Urine drug screen will be done every day in an in-clinic setting to monitor for contraband and every day in an outpatient setting to monitor illicit drug use.
- (l) During in-clinic treatment, resting (sitting [or recumbent if necessary because of an adverse event]) and standing (if able) blood pressure and pulse will be measured before every dose and 3.5 hours after study medication administration at 8 AM, 1 PM, and 6 PM; respiration and temperature before 8 AM dose only.
- (m) During outpatient treatment, resting (sitting [or recumbent if necessary because of an adverse event]) and standing (if able) blood pressure and pulse will be measured before an in-clinic dose of lofexidine each day and 3.5 hours after dosing on Days 4-13 and once before any dose on Day 14 and at the End of Treatment/Study Discontinuation visit. Oral temperature and respiration are not required measurements during outpatient treatment.
- (n) C-SSRS will be completed 3.5 hours after the first dose (8 AM) during in-clinic treatment or once daily before an in-clinic dose of lofexidine during outpatient treatment.
- (o) During in-clinic treatment, effectiveness scales will be completed once daily: the Short Opiate Withdrawal Scale of Gossop 3.5 hours ( $\pm$ 10 minutes) after the first dose of study medication followed by COWS, and the assessment of completion of pre-defined withdrawal treatment goal. Effectiveness scales will be completed daily before an in-clinic dose of lofexidine during outpatient treatment.
- (p) A fingerprick blood sample for PK analysis will be collected concurrently with each scheduled ECG.
- (q) A fingerprick blood sample will be collected during outpatient treatment when the subject reports to the clinic each day (before next scheduled dose) for analysis of plasma lofexidine concentration to monitor compliance.
- (r) This form is to be completed by the Principal Investigator after completion of the SOWS-Gossop and COWS.
- (s) A follow-up telephone contact will be attempted 30 days after the subject's last dose and will include an adverse event evaluation and an evaluation of the subject's current treatment status (e.g., relapse, current psychosocial treatment, successful entry into a methadone, buprenorphine, or naltrexone program).

## 2. SAMPLE SIZE

The total enrollment in this study will depend on subject drop-out rates in this protocol. Enrollment will continue until a minimum total of 300 subjects (across this protocol and earlier lofexidine clinical studies expected to meet FDA safety database requirements) have been treated with clinically relevant doses of lofexidine for a minimum of 7 days. It is estimated that approximately 250 to 500 subjects will be enrolled in this open-label study in order to accrue a sufficiently large safety database for evaluation.

## 3. RANDOMIZATION

No randomization was performed.

## 4. INTERIM ANALYSIS

No interim analysis is planned.

## 5. STATISTICAL METHODS

### 5.1 Continuous

Continuous variables and ordered categorical variables not subject to censoring will be summarized with the number of non-missing observations, mean, standard deviation, minimum, 25th percentile, median, 75th percentile, and maximum.

For summary statistics, means, medians and percentiles will be displayed to one more decimal place than the raw data, dispersion statistics (e.g. standard deviation) will have two more decimal places, and the minimum and maximum will be displayed to the same number of decimal places as reported in the raw data.

### 5.2 Categorical

Unordered categorical and ordered categorical (depending on the number of categories) variables will be presented in contingency tables with cell frequencies and percentages for the number of non-missing observations and frequencies for the number of missing observations apart from disposition of subjects, concomitant medications, measurement of treatment compliance and adverse events where percentages will be presented for the population.

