### **14.3.2 Days 4-7 (In-clinic/Outpatient)**

Per clinical judgment of the Principal Investigator, subjects can continue to receive lofexidine treatment in a clinic setting or can be treated outside of the clinic (outpatient) for the remaining 4 days of mandatory lofexidine treatment (Days 4-7). All subjects receiving lofexidine treatment on an outpatient basis will be required to take a dose of lofexidine in the clinic at each daily clinic visit, with required clinical assessments performed before and after dosing as detailed in [Table 1](#). Subjects not requiring extended lofexidine treatment can be discharged from the study on Day 7 after receipt of at least one dose of study drug and after all end-of-study procedures have been completed (see Section 15.3.4).

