### **14.3.3 Days 8-14 (Outpatient Only)**

Per Principal Investigator judgment, subjects can continue lofexidine treatment on an outpatient basis for up to an additional 7 days. Note that lofexidine dosing may be stopped at any time during Days 8-14. No subject will receive lofexidine for more than 14 days total in this study. Subjects will be required to return to the clinic daily before a scheduled dose for clinical assessments (see a complete list of assessments in [Table 1](#)).

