### **15.3.3 Days 8-14 (Outpatient Only)**

Study medication is optional on Days 8-14 for subjects continuing to have withdrawal symptoms per the Principal Investigator's judgment. The assessments and procedures listed

below will be performed daily (unless otherwise specified) (see Section 15.3.4 for assessments/procedures required for discontinuation from the study).

- Daily clinic visits and completion of subject diary.
- SOWS-Gossop before an in-clinic dose of lofexidine.
- COWS before an in-clinic dose of lofexidine.
- Completion of pre-defined withdrawal treatment goal (e.g., planned detoxification/transition) as assessed by the Principal Investigator (after completion of the SOWS-Gossop and COWS).
- Concomitant medication assessment.
- Pill count and review of subject diary ([Appendix 3](#)) to measure compliance with previous day's doses.
- Vital Signs, including blood pressure and pulse at rest (sitting [or recumbent if necessary because of an AE]) and standing (if able) before an in-clinic dose of lofexidine and 3.5 hours after dosing on Days 8-13 and once before any dose on Day 14. Note that if subjects cannot stay in the clinic for measurement of the 3.5-hour post-dose vital signs required on Days 8-13, they will be given a portable digital blood pressure machine for measurement of their vital signs at this required time point. Subjects will also be provided a diary ([Appendix 3](#)) to record the measurements along with any symptoms of hypotension and/or bradycardia (see list in Section 13.2.2) the subject may have experienced.
- AE assessment.
- Clinical laboratory tests as clinically warranted.
- Complete physical examination as clinically warranted.
- C-SSRS (Since Last Visit Version; [Appendix 6](#)) before an in-clinic dose of lofexidine.
- A fingerprick blood sample will be collected during outpatient treatment when the subject reports to the clinic each day (before next scheduled dose) for analysis of plasma lofexidine concentration to monitor compliance.
- Qualitative urine drug screening (by on-site use of "dipsticks") will be done every day in an outpatient setting to monitor for illicit drug use.

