## 6.3 Analysis populations

The Enrolled Population includes all subjects screened into the study irrespective of whether they received the study medication.

The Safety Population includes all subjects who received at least one dose of study medication.

With the exception of the disposition table all outputs will use the Safety Population.

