### Measurement of Treatment Compliance

Details of compliance will be tabulated overall and for each co-administration category by study day.

Additionally, lofexidine concentration data will be summarized by descriptive statistics for each study day.

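### Daily compliance percentages are divided by everyone ever dosed, so on Days 8-14 any categorical compliance figure shows adherence multiplied by the share still on treatment

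*SAP*

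**What the plan says.** The denominator comes from SAP 5.2 and 6.3. The default in 5.2 is "percentages for the number of non-missing observations and frequencies for the number of missing observations apart from disposition of subjects" and a short list of other outputs. That list includes "measurement of treatment compliance and adverse events where percentages will be presented for the population". SAP 6.3 says which population is meant: "With the exception of the disposition table all outputs will use the Safety Population", and "The Safety Population includes all subjects who received at least one dose of study medication". This number does not change from one study day to the next.

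The layout comes from SAP 6.7.2, under Measurement of Treatment Compliance: "Details of compliance will be tabulated overall and for each co-administration category by study day". Neither section gives a day-specific denominator or a row for subjects no longer on treatment.

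The protocol plans for subjects to stop at different times:

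- Section 14.3.2: "Subjects not requiring extended lofexidine treatment can be discharged from the study on Day 7 after receipt of" one dose or more that day, once the end-of-study procedures are done. SAP 6.6 counts such a subject as having completed the study.
- Section 15.3.3: "Study medication is optional on Days 8-14 for subjects continuing to have withdrawal symptoms per the Principal Investigator's judgment".
- Section 14.3.3: "Note that lofexidine dosing may be stopped at any time during Days 8-14".

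**The concern.** Compliance on a given day can be observed only in subjects who were due to take lofexidine that day. Under the SAP's rule, a subject who took every dose and was discharged on Day 7 as planned remains in the denominator for Days 8 to 14 and can add nothing to the compliant count. The compliant percentage then falls as people leave, even if every remaining subject takes every dose.

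This matters because the primary objective covers outpatient as well as in-clinic use, and outpatient dosing is largely unobserved. The protocol collects pill counts, diaries and fingerprick samples to assess it (Protocol 13.3). A daily percentage that carries retention inside it is a poor summary of that evidence. It also distorts the side-by-side reading of the buprenorphine, methadone and other columns if those groups continue past Day 7 at different rates.

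**Working it through.** The documents state no compliance, dropout or continuation figure, so there is no plan figure to reproduce. The check is direct arithmetic on the stated rule.

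**Inputs from the documents.** The denominator is the Safety Population (SAP 5.2 and 6.3). The table is by study day (SAP 6.7.2). Planned enrollment is about 250 to 500 (SAP 2).

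**Assumed inputs.** The Safety Population is N = 500, with N = 250 as a check. True compliance among those dosing is held constant at 95%, with 90% and 100% as a range. The share still on treatment runs from 100% down to 10%.

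**Formulas.** On day d:

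- SAP rule: displayed % = (number on treatment × compliance among them) / N = compliance × share on treatment.
- On-treatment rule: displayed % = number compliant / number due to dose that day.

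**Results for N = 500 and 95% compliance** (whole subjects):

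| Share on treatment | On treatment | Compliant | SAP rule: compliant | SAP rule: observed non-compliant | On-treatment rule |
|---|---|---|---|---|---|
| 100% | 500 | 475 | 95.0% | 5.0% | 95.0% |
| 80% | 400 | 380 | 76.0% | 4.0% | 95.0% |
| 60% | 300 | 285 | 57.0% | 3.0% | 95.0% |
| 40% | 200 | 190 | 38.0% | 2.0% | 95.0% |
| 20% | 100 | 95 | 19.0% | 1.0% | 95.0% |
| 10% | 50 | 48 | 9.6% | 0.4% | 96.0% |

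The 96.0% in the last row is rounding to whole subjects.

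**Range.** At 90% compliance the SAP rule gives 72%, 36% and 9% when 80%, 40% and 10% remain. At 100% compliance the displayed figure equals the share on treatment. With N = 250, 95% compliance and 40% remaining, it is 95/250 = 38.0%, so N does not drive the result.

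**Comparison between categories.** Take two co-administration groups, each 95% compliant, with 60% of one and 20% of the other continuing (assumed). The table would show 57% and 19%, a gap of 38 points, although adherence is identical.

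**Rows do not close.** If a non-compliant row is filled only from subjects with data, it shrinks too. At 40% remaining, the two rows add to 38% + 2% = 40%, and the other 60% of subjects appear in neither.

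**The case against.** A reader might infer that the SAP classes leavers as non-compliant. It does not. It says only what the percentages are divided by. The defect is a compliant percentage diluted by people who had no dose due, and rows that need not add to 100%.

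Compliance is also not defined. Pill counts and plasma concentrations are naturally numeric, and a numeric summary would follow SAP 5.1, which reports the number of non-missing values. The artefact would then not arise. This stands as a limit: the point applies only to categorical compliance output. But 5.2 names compliance among the outputs shown as percentages, so such output is contemplated.

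On Days 1-7 treatment is mandatory, and subjects are expected to continue through Day 7 even if their goal is met sooner (Protocol 15.4.1). A whole-population denominator is arguable there, as the share of all dosed subjects taking drug as planned. That is fair, provided the table says that this is what it shows.

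A reader might also infer that retention and adherence could not be separated anywhere in the report. The documents do not support that. SAP 5.2 shows frequencies beside percentages, 6.6 gives Day 7 completion and withdrawal reasons, and 6.9 gives days of exposure and missed doses with reasons by subject and day. These help a careful reader but do not correct the compliance percentage.

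Finally, SAP sections 7 and 8 as published show only column headers. Table shells might carry daily counts, but this cannot be checked, and the written rule would still govern the percentage.

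**Conclusion.** The point holds. It concerns a stated rule that gives a misleading figure, not a missing detail. For categorical compliance, SAP 5.2, 6.3 and 6.7.2 together make the daily percentage equal to adherence times the share still on treatment. The anomaly is clear on Days 8-14, where stopping is planned. On Days 1-7 the figure mixes early discontinuation with adherence, which can be defended if labelled.

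The direction is certain once anyone has stopped. The size is not known: 95% compliance shows as 76% if 80% remain and 38% if 40% remain, but these shares are assumptions. The consequence is limited to a descriptive table. Compliance is not a listed safety or effectiveness endpoint, and no test between co-administration categories is planned.

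**What to change.** In SAP 5.2, remove treatment compliance from the outputs whose percentages use the population. In SAP 6.7.2, state that each study day's denominator is the number of subjects scheduled to receive lofexidine that day, and show that n in every column. Show subjects discharged or discontinued by that day as a separate count, so that retention stays visible. Say in the same place how compliance is defined and whether it is categorical or numeric.

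No new data are needed. The cost is SAP wording and a small derivation rule. Actual dose dates and times are explicitly on the eCRF for in-clinic doses (Protocol 13.2.1). For outpatient days the rule must draw on diaries and dispensing logs (Protocol 12.2 and 12.6), because one to two days of tablets may be dispensed at a visit. It should also cover the discharge day, since a subject may leave on Day 7 after only one of that day's four doses.

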## 6. ANALYSIS PLAN

### 6.1 General

The treatment will be labelled as Lofexidine for presentation of efficacy and safety data. Subject data in [Appendix 16.2](#) listings will be ordered by treatment, site, subject, and study day when applicable.

All tabulations, data listings and figures will be produced using SAS Version 9.3 or higher.

All summaries and analyses documented below will be presented in the final integrated statistical/clinical report and tables that will be based on the E3 guidelines published by ICH.

However, it is noted here that no analysis plan prepared in advance of the data can be absolutely definitive and so the final report may contain additional tables or statistical tests if warranted by the data obtained. The justification for any such additional analyses will be fully documented in the final report.

## 6.2 Derived Data

- Definition of baseline

With the exception of vital signs measurements, baseline is defined as the last non-missing value prior to the receiving the first dose of study medication. For vital signs measurements, the last screening measurement will be used as baseline.

All tabulations involving change from baseline data will only include subjects with cohort data i.e. with data at baseline and at follow-up. Change from baseline will be calculated as follow-up values minus baseline value.

- Incomplete dates

All incomplete dates will be included in the clinical database as they were entered in the eCRF. Thereafter for calculation purposes, the incomplete dates will be completed using pre-defined rules. If a day or month is not recorded it will be replaced by the first day of the month or January respectively, provided this does not contradict any other dates recorded. For missing adverse events and medications dates/times during the trial, the worst-case date will be used (e.g. the end of the month for a stop date and 23:59 for the stop time, the date/time of initial dose for start of AE i.e. all events with missing start dates will be assumed to be treatment emergent).

- Ambiguous values

In the case where a variable is recorded as “ $>x$ ”, “ $\geq x$ ”, “ $<x$ ” or “ $\leq x$ ”, then for analysis purposes a value of x will be taken. Where a range of values is quoted the midpoint of the range will be taken.

- Questionnaire Data

In the event that component items used to calculate total scores for questionnaire data e.g. SOWS Gossop score are missing then the total scores will also be set to missing.

